5.5.3 Analysis of Exploratory Efficacy Endpoint

Exploratory efficacy endpoint includes log10-transformed viral load at each visit as measured by TCID₅₀ for replication competent virus via both expelled saliva specimen and oropharyngeal swab collection methodologies. The sponsor will analyze the data collected for each biospecimen after the study is unblinded and provide details on the R&D test method and geometric means for inclusion in the complete study report.

5.6 Safety and Tolerability Variables and Analyses

Safety and tolerability analyses will be performed for the Safety Population. All safety listings and tables will be stratified by treatment assignment.

5.6.1 Adverse Events

All adverse events (AEs) occurring during the study will be recorded and coded in the Medical Dictionary for Regulatory Activities (MedDRA), version 22.1 or higher. TEAEs are defined as AEs recorded after first application of the study treatment.

Frequency and percent of subjects reporting TEAEs will be tabulated for each treatment by system organ class (SOC) and preferred terms (PT) for the following:

- all TEAEs
- all TEAEs by severity
- all TEAEs by relationship to study treatment

In the summaries of incidence (frequencies and percentages) of all TEAEs, subjects who report more than one event that are mapped to the same PT will be counted only once. In the summaries of incidence of TEAEs by severity and by relationship to study treatment, subjects who report more than one event that are mapped to the same PT will be counted only once under the strongest severity and relationship, accordingly. The composite of study subjects captured in this analysis will then be tabulated by what study day the 'most severe' observation was made.

Tabulations will be generated for solicited AEs (reactogenicity) separate from unsolicited AEs. Numbers and percentages of illumination site reactions, as well as unsolicited AEs, will be tabulated for each study day 1 through 8 so daily AE point prevalence may be determined. Likewise, tabulate oropharyngeal assessment overall and for each study visit.

Treatment-Emergent Serious Adverse Events (TESAEs) will be discussed within the clinical study report. TEAEs, TESAEs and TEAEs that led to treatment interruption or discontinuation will be presented in data listing.

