All AEs were of short duration, with resolution typically reached the same day or within 24 hours. Since study subjects used the RD-X19 device approximately every 12 hours for 14 contiguous days, there was a continuous temporal association with RD-X19 device use and incident AEs during the course of RD19-01-3Q20. By definition, all local site reactions were attributed to the device; all were mild and transient and there was no pattern of increasing frequency with repeated, cumulative dosing.

Population-based epidemiological data for headaches and nausea were considered when establishing device attribution. Approximately 40% of the general adult population have weekly headache and over 30% suffer from intermittent bouts of nausea of unknown origin. Given the frequencies of headache and nausea reported in RD19-01-3Q20 are less than those reported in population-based epidemiological studies, the relationship with the RD-X19 device cannot be determined.

In summary, the RD19-01-3Q20 Phase I trial demonstrated that EmitBio™ RD-X19 is a safe device, consistent with the sponsor's and IRB's original conclusion that RD-X19 is a NSR device.

Risks to Privacy

Subjects will be asked to provide personal health information (PHI). All attempts will be made to keep this PHI confidential within the limits of the law. However, there is a chance that unauthorized persons will see the subject's PHI. All study records will be kept in a locked file cabinet or maintained in a locked room at the participating clinical trial site(s). Electronic files will be password protected. Only people who are involved in the conduct, oversight, monitoring, or auditing of this trial will be allowed access to the PHI that is collected. Any publications from this trial will not use information that will identify subjects by name.

Organizations that may inspect and/or copy research records maintained at the participating clinical trial site(s) for quality assurance (QA) and data analysis include groups such as the IRB and the FDA.

A description of this clinical trial will be posted on <http://www.ClinicalTrials.gov>. This web site does not include information that can identify subjects.

There may be other risks, discomforts or side effects that are entirely unknown at this time.

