 - Number of subjects experiencing an SAE or Grade 3 AE, in the same SOC grouping of Preferred Terms based on Medical Dictionary for Regulatory Activities (MedDRA) coding, considered to be related to RD-X19.

Safety and tolerability (local reactogenicity) will be assessed actively on each clinic visit by review of potential adverse events (AEs) and targeted physical examination, as required. Volunteers will be encouraged to contact designated clinical trial staff for AEs of a medically-urgent nature as soon as is practically possible and to seek immediate medical care, if needed.

Metabolic, liver, kidney and hematological laboratory evaluations will be performed at screening and at Day 8 or early termination (and potentially during unscheduled) clinic visits.

Study Subject safety will be monitored throughout the study by the Investigator and supported by regular review by the Medical Monitor and an external Data Monitoring Committee.

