 - Subjects will be observed in the clinic for at least 30 minutes post the first RD-X19 illumination. The oropharynx and surrounding tissues will be examined. Reactogenicity assessments will be performed on Days 1, 2, 3, 5, and 8. An oropharyngeal examination will also be performed on Days 1 and 8 and during unscheduled visits and early termination visits and recorded on the appropriate source document prior to discharge from the clinic. Interim or unscheduled oropharyngeal examinations will be performed, if necessary, to evaluate AEs.
- Vital signs:

Vital sign measurements will include systolic and diastolic BP, HR, **RR**, and oral temperature. Vital signs will be measured at timepoints specified in protocol section 4.2. Subjects must not eat or drink anything hot or cold within 10 minutes prior to taking their oral temperature or using the RD-X19 device.
- Clinical laboratory evaluations:
 - Fasting is not required before collection of clinical laboratory evaluations.

- Urine pregnancy test will be performed locally by the site laboratory at the screening visit and at the final study visit. Results must be confirmed as negative prior to randomization on Day 1 and allocation and use of the RD-X19 device.
- Clinical laboratory evaluations CMP and CBC (diff) will be performed locally by the site selected laboratories.
 - Clinical safety laboratory evaluations will be performed locally by the site laboratory.
 - Blood and urine will be collected at timepoints specified in the protocol section 4.2.

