3.1 Study Design

For the purpose of exploring the above objectives, the study will be conducted as a randomized, double-blind, sham-controlled dose escalation study in SARS-CoV-2 infected individuals with outpatient COVID-19 at two dosing schedules.

This study plans to enroll into two treatment arms within two escalating dose cohorts:

Volunteers meeting all inclusion criteria and none of the exclusion criteria will be randomized to the RD-X19 treatment arm or the sham treatment arm within each cohort in a 2:1 ratio (20 RD-X19 : 10 sham), according to a fixed schedule via a permuted block design and stratified by clinical site. Light will be administered twice daily locally to the mouth and throat only for four days for Cohort 1 and for seven days for Cohort 2.

The clinic visits will occur at:

- Visit 1 / Screening, Enrollment & Randomization

- Visit 2 / Day 2
- Visit 3 / Day 3
- Visit 4 / Day 5 (\pm 1 day)
- Visit 5 / Day 8 (\pm 1 day) / Early Termination (ET)

Assessments of treatment response will occur on study days 3 and 5, with a final determination of efficacy made on day 8 (inclusive).

Efficacy will be evaluated through evaluation of viral load through quantitation of SARS-CoV-2 mRNA by RT-qPCR and via quantitation of replication competent virus by viral titer. Severity of the symptoms of disease will also be aggregated to produce a composite COVID-19 severity score. Safety and tolerability assessments will include solicited and unsolicited adverse events (AEs), physical examinations, vital signs, and clinical laboratory tests.

One unblinded interim analysis is planned upon completion of all subjects in Cohort 1. The results of the interim analysis will be reviewed by a safety monitoring team and a recommendation will be made to the sponsor on whether enrollment should proceed for the next cohort at the next planned dose or at a reduced dosing frequency (e.g. once daily). The study is designed to evaluate at least 2 dosing schedules, ascending, or descending based on safety of each previous cohort.

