5.1 Methodological Considerations

General Conventions

SAS software (version 9.4 or higher) will be used for all data analyses and tabulations.

The study is not powered for hypothesis testing. P-values will be considered descriptive and will not be adjusted for multiplicity.

Data for all investigational centers will be pooled for analysis.

Unless specified elsewhere, baseline is defined as the last available measurement prior to administration of study drug. Change from baseline will be calculated as the post-baseline value minus the baseline value.

Summary tables will include the data based upon the protocol scheduled time points. For subjects who are early discontinued from the study, all efficacy assessments captured at the ET visit will be assigned to the nearest protocol scheduled time point.

Visit of Treatment Period	Range*	Target Day
Visit 1 / Baseline (Day 1)	Study Day = 1	Day 1
Visit 2 / Day 2	Study Day = 2	Day 2
Visit 3 / Day 3	Study Day = 3	Day 3
Visit 4 / Day 5 (± 1 day)	Study Day 4 to 6	Day 5
Visit 5 / Day 8 (± 1 day)	Study Day 7 to 9	Day 8

*Study day = date of visit - date of first treatment + 1

Descriptive statistics of continuous variables will include n, mean, standard deviation (SD), median, minimum and maximum. Generally, the minimum and maximum values will be presented to the same decimal precision as the raw values, the mean and median values to one more, and the SD, to two more decimal places than the raw values. Summaries for categorical data will include frequencies and percentages. Percentages will be presented to one decimal place.

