Counts reflect numbers of subjects reporting one or more TEAE that map to the MedDRA system organ class/preferred term. At each level of summarization (system organ class or preferred term), subjects reporting more than one TEAE are counted only once under the earliest Study Day when the event of greatest severity was reported.

Source: Listing 16.2.7

O:\Studies\EmitBio\EB-P12-01\Biometrics\Programs\Tables\xxx.sas ran on Month Day, Year at hh:mm on data from Month Day, Year.

Table 14.3.2 – Reactogenicity by Visit for Safety Population

Study Visit	Category	4 Days RD-X19 n (%)	7 Days RD-X19 n (%)	Sham n (%)
Visit 1 /Day 1	N	XX	XX	XX
	n (%) subject with illumination site pain	XX (XX.X)	XX (XX.X)	XX (XX.X)
	n (%) subject with illumination site erythema	XX (XX.X)	XX (XX.X)	XX (XX.X)
	n (%) subject with illumination site Edema/Induration	XX (XX.X)	XX (XX.X)	XX (XX.X)
	n (%) subject with other pain, redness, swelling, or lesion of the oral mucosa	XX (XX.X)	XX (XX.X)	XX (XX.X)
Visit 2 /Day 2	N	XX	XX	XX
	n (%) subject with illumination site pain	XX (XX.X)	XX (XX.X)	XX (XX.X)
	n (%) subject with illumination site erythema	XX (XX.X)	XX (XX.X)	XX (XX.X)
	n (%) subject with illumination site Edema/Induration	XX (XX.X)	XX (XX.X)	XX (XX.X)
	n (%) subject with other pain, redness, swelling, or lesion of the oral mucosa	XX (XX.X)	XX (XX.X)	XX (XX.X)
Visit 3 /Day 3	...			
Visit 4 /Day 5	...			
Visit 5 /Day 8/ET	...			

Source: Listing 16.2.9.1

O:\Studies\EmitBio\EB-P12-01\Biometrics\Programs\Tables\xxx.sas ran on Month Day, Year at hh:mm on data from Month Day, Year.

Table 14.3.3 – Oropharyngeal Assessment by Visit for Safety Population

Study Visit	Category	4 Days RD-X19 n (%)	7 Days RD-X19 n (%)	Sham n (%)
Overall*	N	XX	XX	XX
	Normal	XX (XX.X)	XX (XX.X)	XX (XX.X)
	Abnormal	XX (XX.X)	XX (XX.X)	XX (XX.X)
Visit 1 /Day 1	N	XX	XX	XX
	Normal	XX (XX.X)	XX (XX.X)	XX (XX.X)
	Abnormal	XX (XX.X)	XX (XX.X)	XX (XX.X)
Visit 2 /Day 2	N	XX	XX	XX
	Normal	XX (XX.X)	XX (XX.X)	XX (XX.X)
	Abnormal	XX (XX.X)	XX (XX.X)	XX (XX.X)
Visit 3 /Day 3	...			
Visit 4 /Day 5	...			
Visit 5 /Day 8/ET	...			

*For Overall, Normal category includes subjects with a normal result for all visits; Abnormal category includes subjects with an abnormal result at any visit.

Source: Listing 16.2.9.2

O:\Studies\EmitBio\EB-P12-01\Biometrics\Programs\Tables\xxx.sas ran on Month Day, Year at hh:mm on data from Month Day, Year.

Table 14.3.4 – Vital Signs by Visit for Safety Population

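### The SAP promises illumination-site reactions for each of study days 1 to 8, but its tables are by visit and Days 4, 6 and 7 have no scheduled same-day assessment

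*Combined protocol and SAP*

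**What the plan says.** SAP 5.6.1 separates solicited from unsolicited events and states that numbers and percentages of illumination-site reactions "will be tabulated for each study day 1 through 8 so daily AE point prevalence may be determined".

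The collection schedule is in protocol version 2.0. Section 9.2: "Reactogenicity assessments will be performed on Days 1, 2, 3, 5, and 8". Section 6.1 ties local tolerability to the visits: it "will be assessed actively on each clinic visit by review of potential adverse events (AEs) and targeted physical examination, as required". Section 9.2.2 lists four solicited items and says they are obtained by asking the subject throughout the study, but schedules no contact between visits. The diary, as sections 9.3 and 9.3.1 describe it, holds COVID-19 symptoms and completed treatments, not site reactions.

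The output is Table 14.3.2. Its rows are the visits on Days 1, 2, 3 and 5 and a combined Day 8/early-termination visit. Each visit has four items, for example "n (%) subject with other pain, redness, swelling, or lesion of the oral mucosa". Its source, Listing 16.2.9.1, has subject, cohort, visit and the four items, with no date and no grade.

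On exposure, SAP 3.1 has light given "twice daily locally to the mouth and throat only for four days for Cohort 1 and for seven days for Cohort 2". On Phase I experience, protocol 5.2.1 says: "All AEs were of short duration, with resolution typically reached the same day or within 24 hours".

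**The concern.** The SAP commits to a daily statistic, but the form, listing and table meant to carry site reactions are not daily. The gap also falls unevenly. Cohort 2 differs from Cohort 1 in treatment duration, so Days 5–7 are where any effect of continued light on the mouth and throat would first show, and those days have the thinnest same-day questioning. If the daily table is produced anyway, a low count on Days 4, 6 or 7 could mean few reactions or few opportunities to record one, and a reader could not tell which.

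A smaller problem is that Table 14.3.2 places every early-termination assessment in the Day 8/ET row. The SAP 5.1 rule that moves early-termination data to the nearest scheduled time point covers efficacy assessments only. An early-termination assessment made on Day 4 or 6 would therefore be shown beside true Day 8 assessments.

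**Working it through.** The plan gives no figure of its own here, so the check is a count of days.

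**Inputs**
- Days promised: 1 to 8 (SAP 5.6.1).
- Days assessed, nominal: 1, 2, 3, 5, 8 (protocol 9.2).
- Visit windows: Visit 4 is "Study Day 4 to 6" and Visit 5 is "Study Day 7 to 9" (SAP 5.1).
- Treatment days: 1–4 in Cohort 1 and 1–7 in Cohort 2 (SAP 3.1). SAP 5.1 counts study days from first treatment, so dosing starts on Day 1 and the extra days are 5–7.
- Sessions: 4 × 2 = 8 in Cohort 1 and 7 × 2 = 14 in Cohort 2, a difference of 6.

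**Nominal schedule**
- Promised days with an assessment: 5/8 = 62.5%. Days 4, 6 and 7 have none.
- Days 1–4: 3/4 = 75%.
- Days 5–7: 1/3 = 33% (Day 5 only).

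**All nine window combinations**

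| Visit 4 on Day | Visit 5 on Day | Days 1–4 assessed | Days 5–7 assessed | Days 1–8 assessed |
|---|---|---|---|---|
| 4 | 7 | 4/4 | 1/3 | 5 |
| 4 | 8 | 4/4 | 0/3 | 5 |
| 4 | 9 | 4/4 | 0/3 | 4 |
| 5 | 7 | 3/4 | 2/3 | 5 |
| 5 | 8 | 3/4 | 1/3 | 5 |
| 5 | 9 | 3/4 | 1/3 | 4 |
| 6 | 7 | 3/4 | 2/3 | 5 |
| 6 | 8 | 3/4 | 1/3 | 5 |
| 6 | 9 | 3/4 | 1/3 | 4 |

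Coverage of Days 5–7 never reaches that of Days 1–4, and no subject has more than 5 of the 8 days assessed. A Visit 4 row can also mix Day 4 with Day 6, so a count by visit is not a count by study day.

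**Recall needed for the other days.** Nominally, Day 4 is asked about on Day 5 (1 day back), and Days 6 and 7 on Day 8 (2 and 1 days back). In the widest case, with visits on Days 4 and 9, Day 5 is recalled from 9 − 5 = 4 days away.

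**Do other outputs fill the gap?** Table 14.3.1.4 counts each subject once, on the day of the most severe observation. That is not the number of subjects with a reaction present on a given day. Listing 16.2.7 has start and stop study days and intensity, so prevalence could be derived from it, but no table or rule does so. The SAP's interim section says all 5.6.1 safety tabulations will be assessed. Its package has Table 14.3.2, Listing 16.2.9.1 and Listing 16.2.7, but no by-day table, not even 14.3.1.4.

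**Illustration only.** Assume, since the documents give no rate, that reactions last less than a day, are independent between days, and occur with probability p per day in 20 subjects on the nominal schedule. Expected subjects with at least one reaction on Days 5–7 are 20 × [1 − (1 − p)³]; those reacting on Day 5 number 20p.

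| p | Any on Days 5–7 | On Day 5 |
|---|---|---|
| 0.05 | 2.85 | 1.0 |
| 0.10 | 5.42 | 2.0 |
| 0.20 | 9.76 | 4.0 |

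This is what same-day questioning alone would see, with no recall. The true loss is smaller to the extent that reactions are remembered and dated.

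**The case against.** The strongest reply is that a dated, graded source already exists. Solicited reactions are AEs. Protocol 9.2.1 asks for onset, severity and resolution of every AE, solicited ones included, and 9.2.9 adds start and stop dates, each intermittent episode and changes in severity. This stands: a reader might infer that Days 4, 6 and 7 are simply unobserved, and the documents do not support that. What is missing is a same-day assessment and a stated derivation. On the nominal schedule recall is only one or two days.

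Other daily signals exist. Sore throat is self-rated twice daily, and Clarification Memorandum #1 sends new COVID-consistent symptoms from Day 4 onward to the AE forms. Both overlap with local pain but are confounded with the disease, and the memo changes the recording route between Days 3 and 4, so neither replaces a site-reaction count.

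The primary safety measure concerns device-related serious events and patterns of grade 2 or higher, which are less easily forgotten than mild soreness. Phase I used the device about every 12 hours for 14 days and saw no rise in frequency with cumulative use, although its dose is redacted and its subjects were healthy. These points limit the weight of the issue without removing the mismatch.

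A reader might also infer that a mouth reaction that stops a subject on Day 3 would be displayed as a Day 8 reaction. That does not follow, because Day 3 has its own visit and row. The pooling matters for early-termination assessments off the visit days. The row is labelled ET, and the exit day is in Listing 16.2.1.

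**Conclusion.** The mismatch holds: SAP 5.6.1 specifies a daily prevalence that the SAP's own tables do not produce and that scheduled questioning supports on 5 of 8 days at most. Same-day coverage is lower on Cohort 2's extra treatment days (1 of 3 nominally, range 0 to 2) than on Days 1–4 (3 or 4 of 4). Partial reconstruction from AE records is possible, but it depends on recall of reactions that tend to be short.

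It is tempting to conclude that the longer schedule will look better tolerated than it is. The documents do not support this. Active and sham subjects share the visit schedule, and nothing in the documents gives the reaction rate or the completeness of recall, so the direction and size of any bias against sham are unknown.

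The count assumes that dosing starts on Day 1 and that visits fall within the SAP windows. Duration may not be the only exposure difference between cohorts, since the dose values are redacted. The point concerns the correctness of a planned safety table, not the primary safety measure, and is worth correcting because correction is cheap.

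**What to change.** **In the SAP and the interim package.** Add a table of illumination-site reactions by actual study day (1–8) and grade, derived from dated AE records.
- Count a subject on day d if a reaction started on or before d and had not stopped before d.
- Use the number of subjects still under observation on day d as the denominator.
- Place early-termination reactions on their actual study day.
- State how a missing stop date is handled; SAP 5.2.2 treats only partial start dates for AEs.
- Footnote which days rest on recall.

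Add study day and grade to Listing 16.2.9.1. The cost is one table, two listing columns and a short derivation rule. SAP section 6 already allows the shells to be modified.

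**Where data collection can still change.** Add the four solicited items of protocol 9.2.2, graded, to the existing twice-daily diary, in both arms of a cohort. The cost is a diary and eCRF revision and a small added burden at each entry. If the items come in for Cohort 2 only, ascertainment will differ between cohorts. Diary-based rates should then be compared with the concurrent Cohort 2 sham, not across cohorts. Because Table 14.3.2 has a single sham column, sham would have to be shown by cohort in that table.

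**Minimum, if neither is done.** Restrict the 5.6.1 statement to the scheduled visits, so that the text matches the table.

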5.6.2 Vital Signs

For each vital sign (systolic and diastolic blood pressure, heart rate, and oral temperature), actual values and change from baseline values will be summarized using descriptive statistics for each treatment group by visit.

5.6.3 Methemoglobin

Actual values of methemoglobin at baseline and Day 8/ET as well as change from baseline values will be summarized using descriptive statistics for each treatment group.

5.6.4 Other Assessments

Following assessment results will be presented in subject data listing: medical history, physical examination, clinical laboratory evaluations, concomitant medications.

Interim Analysis

Upon completion of all subjects in Cohort 1, an unblinded interim analysis will be conducted focusing on the following evaluations:

- Efficacy:
 - Geometric mean viral load as measured in saliva on day 1, 3, 5 and 8 by RT-qPCR
 - Proportion of subjects demonstrating viral load reduction $\geq 95\%$ on day 3, 5 and 8 by RT-qPCR.
 - Time to alleviation of COVID-19 signs and symptoms
 - Time to sustained alleviation of COVID-19 signs and symptoms
- Safety:
 - All safety tabulations as listed in section 5.6.1 will be assessed as part of the interim analysis.
 - Summary of Treatment Emergent Adverse Events including a review of listings to monitor:
 - Number of study subjects experiencing any Serious Adverse Reaction (SAE).
 - Number of study subject experiencing treatment site reactions, including pain, induration or erythema of the oropharynx or oral mucosa, including the uvula and tongue.
 - Number of study subjects with any laboratory result that is out-of-range using the testing laboratory's institutional standards, including blood, urine and methemoglobin measured by pulse oxymetry.
 - Number of subjects experiencing laryngospasm, bronchospasm or anaphylaxis within 2 hours after use of the RD-X19 Device that is considered related to RD-X19.
 - Number of subjects experiencing an allergic reaction such as generalized urticaria (defined as occurring at three or more body parts) within 72 hours after use of study treatment that is considered related to RD-X19.
 - Number of subjects experiencing Grade 3 TEAE, in the same SOC grouping of PT, considered to be related to RD-X19.

As study subjects in cohort 1 are essentially a separate study, there is no prohibition to sponsor being unblinded for the interim analysis. Cohort 1 subjects are not tied to cohort 2 in any way and unblinding data from cohort 1 has no operational or statistical implications for cohort 2 assessment by sponsor. Study site personnel may not be unblinded to cohort 1 as there is a reasonable possibility that this information could be the basis for bias in the assessment of cohort 2.

To meet above review interest, the following summary tables (treatment groups: 4 Days RD-X19 vs. Sham) and by-subject data listings will be prepared for the interim analysis:

Tables / Listing	Description	Population
Efficacy		
Table 14.1.3	Demographic and Baseline Characteristics	Safety Population Cohort 1
Table 14.2.1.1	Time-Weighted Average Change in Log10-Transformed Viral Load by RT-qPCR from Baseline to Day 8	ITT Population of Cohort 1
Table 14.2.2.1	Log10-Transformed Viral Load via RT-qPCR by Visit	ITT Population of Cohort 1
Table 14.2.2.3	Proportion of Subjects with At Least 95% Reduction by Visit in SARS-CoV-2 Viral Load via RT-qPCR	ITT Population of Cohort 1
Table 14.2.5.1	Time to Alleviation of COVID-19 Symptoms	ITT Population of Cohort 1
Table 14.2.5.2	Time to Sustained Alleviation of COVID-19 Symptoms	ITT Population of Cohort 1
Safety		
Table 14.3.1.1	Treatment-Emergent Adverse Events by System Organ Class and Preferred Term	Safety Population of Cohort 1
Table 14.3.1.2	Treatment-Emergent Adverse Events by System Organ Class, Preferred Term and Severity	Safety Population of Cohort 1
Table 14.3.1.3	Treatment-Emergent Adverse Events by System Organ Class, Preferred Term and Causality to Study Device	Safety Population of Cohort 1
Table 14.3.2	Reactogenicity by Visit	Safety Population of Cohort 1
Table 14.3.3	Oropharyngeal assessment by Visit	Safety Population of Cohort 1
Listing 16.2.7	Adverse Events	Cohort 1 subjects
Listing 16.2.8.1	Out-of-Range Results of Clinical Laboratory Tests	Cohort 1 subjects
Listing 16.2.9.1	Reactogenicity Assessment	Cohort 1 subjects
Listing 16.2.9.2	Oropharyngeal Assessment	Cohort 1 subjects
Listing 16.2.9.6	Methemoglobin Measurement	Cohort 1 subjects

6 Tables and Listings

The following is an example of tables, listings and figures that will be included in the clinical study report. They may be modified as needed during the data analyses.

7 Appendices

